**Effect of Vitamin D3 on Lung Function and Exercise
Tolerance in D3 Deficient COPD Patients**

ClinicalTrials.gov ID: NCT03781895

Document Date: December 23, 2018

PROJECT SUMMARY

Background: Chronic Obstructive Pulmonary Disease (COPD) is a major cause of morbidity and mortality throughout the world which is a preventable as well as treatable disease. It has some important extra pulmonary effects which may contribute to the magnitude of the severity of this disease. Standard therapeutic treatment alone does not optimize its remedy. Vitamin D₃ has been found to improve the physical efficiency of patients with various morbid disorders, including respiratory ailments. **Objectives:** To evaluate the effects of Vitamin D₃ on lung functions and exercise tolerance in patients with stable moderate COPD. **Methods:** For this, a prospective interventional randomized double blinded study will be carried out on 46 (eighty) vitamin D₃ deficient (serum 25 dihydroxycholecalciferol less than 30 ng/ml), male, stable (diagnosed patient, who has not experienced any acute exacerbation, hospitalizations, urgent care visits, or changes in routine medication within 4 weeks prior to study), moderate (post bronchodilator FEV₁/FVC < 0.70 of predicted value and FEV₁ = 50 to 79% of predicted value) COPD patients (age ≥ 40 years), who will be selected from the Out Patient Department (OPD) of the National Institute of Diseases of Chest and Hospital (NIDCH) and will be grouped as A (control) and B (study) groups, respectively. All the patients will be again designated as A0, A90 (with placebo) and B0, B90 (with D₃) for before and after 90 days of follow up. All the participants will be matched in terms of duration of COPD, history of smoking, occupation and socioeconomic status. Along with the standard pharmacological treatment of COPD, the patients of the 'Study group' will be prescribed for 80000 IU of oral vitamin D₃ per week for consecutive 3 months. Along with this, all patients both the groups will be advised to continue ad lib (according to their own choice) diet. At the very 1st day of the study, the lung functions will be assessed by measuring Forced vital capacity (FVC), Forced expiratory volume in one second (FEV₁), Forced expiratory ratio (FEV₁/FVC%), Peak expiratory flow rate (PEFR) and Forced mid expiratory flow of FVC (FEF_{25-75%}), with a portable digital spirometer. In addition, exercise tolerance will be assessed by change in 6 Minute Walk Distance (6MWD) in 6 Minute Walk Test (6MWT). Changes in peripheral capillary oxygen saturation (SpO₂) by Pulse Oximeter and degree of dyspnoea by Modified Borg Scale (MBS) will also be measured both before and after 6MWT to evaluate their change in both the groups. All these variables will be measured again after 90 days standard pharmacological treatment of COPD with D₃ intervention (B group) and also without D₃ intervention (A group). For statistical analysis, Chi-square test, independent sample 't' test between two groups, paired

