Alternate: Vitamin D₃ administration improves lung function and exercise tolerance in vitamin D₃ deficient stable COPD patients.

Objectives:

General Objective

To evaluate the effects of vitamin D₃ administration on lung functions and exercise tolerance in vitamin D₃ deficient male patients with stable COPD.

Specific Objectives

[figure not shown]
- To measure the FVC, FEV₁, FEV₁/FVC%, PEF and FEF_{25-75%} of vitamin D₃ insufficient male patients with stable moderate COPD, in order to assess their lung function status.
- To measure the SpO₂ at rest, in order to assess the basal oxygenation status in this group of patients.
- To determine level of dyspnea at rest, in order to assess the basal breathlessness level in the same group of patients
- To measure the 6MWD of all the patients, in order to assess their functional exercise capacity.
- To measure both the SpO₂ and level of dyspnea again after 6MWT, for the assessment of their exercise tolerance.
- To measure all these variables after 90 days standard pharmacological treatment with vitamin D₃ and also without vitamin D₃ in stable COPD patients.
- To compare the results of baseline and endline.

Methodology:

Consolidated Standard of Reporting Trials:

(Moher et al 2010)

CONSORT 2010 Flow Diagram

TYPE OF STUDY : Prospective interventional randomized double blinded study

PLACE OF STUDY : Department of Physiology, Bangabandhu Sheikh Mujib Medical University (BSMMU), Shahbagh, Dhaka

STUDY PERIOD : March 2017 to February 2018

STUDY POPULATION : Stable, moderate COPD patients with vitamin D₃ deficiency.

SAMPLE SIZE : 46

SAMPLING : Simple random sampling .

GROUPING OF THE SUBJECTS :

Group A : 23 D₃ deficient COPD patients without D₃ administration
(Control group)

A0 : On day 0

A90 : On day 90

Group B : 23 D₃ deficient COPD patients with D₃ administration
(Study group)

B0 : On day 0

B90 : On day 90

Subject Selection:

Inclusion Criteria

- Age: >40 years (Heideri 2015)
- Socioeconomic condition: Middle class (Martineau et al 2015)
- Smoking status: (Janssens et al 2010)
 - Current smoker = with history of active smoking
 - Ex-smoker = with history of 0 – 8 quit year
 - Duration = for >30 pack years
- BMI: 25 – 29.9 kg/meter-sq (Janssens et al 2010)
- COPD patients at moderate stage according to GOLD criteria with > 4 years duration (Rees et al 2013)
- Stable COPD patients (Mehrparver et al 2010)
- Vitamin D₃ deficient: 30 ng/ml (Vitamin D Council 2017)

Exclusion Criteria

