All the above mentioned variables will be similar ,statistically non significant in both the groups to ensure the minimization of their effects.

VITAMIN ADMINISTRATION :

Collection:

Vitamin D3

Ingredient

- Cholecalciferol (40,000IU)
- Microcrystalline Cellulose (58.1 gm)
- Butylated Hydroxy Toluene (0.2mg)
- Magnesium Stearate (3mg)
 - Gelatin Capsule Shell (1mg)

Dose : 80,000 IU/wk

Route : Oral

Placebo : Courtesy of Beximco Pharmaceuticals Limited Bangladesh

Ingredient : • Microcrystalline Cellulose (303.8gm) • Butylated Hydroxy Toluene (0.2mg)

- Magnesium Stearate (3mg)
- Gelatin Capsule Shell (1mg)

STUDY VARIABLES:

(1) Spirometric variables

- FVC (L) : Forced Vital Capacity
- FEV₁ (L) : Forced Expiratory Volume in 1st second
- FEV₁/FVC Ratio (%) : Forced Expiratory Ratio
- PEF_R (L/min) : Peak Expiratory Flow Rate
- FEF₂₅₋₇₅ (L/S) : Forced Expiratory Flow in the middle of FVC

(2) Oxygenation variables

- Resting SpO₂ (%) : Resting Peripheral Capillary Oxygen saturation

(3) Exercise tolerance variables

- 6MWD (meter) : Six Minute Walk Distance
- Level of Dyspnea : Modified Borg Scale

(4) Hematological variables

- 25(OH)D (ng/ml) : 25-hydroxycholecalciferol
- PTH (pmol/l) : Parathyroid hormone
- Ca²⁺ (mg/ml) : Ionic calcium
- PO₄³⁻ (mg/ml) : Ionic phosphate
- AP (U/L) : Alkaline Phosphatase

Subsequently a standard therapeutic treatment (according to GOLD guideline) (Annexure - VI) will be prescribed to all the selected stable moderate COPD patients. In addition, the patients of

the 'Study group' will be prescribed for 80000 IU of oral vitamin D₃ per week for consecutive 90 days . Along with this, all the patients of both the groups will be advised to continue ad lib (according to their own choice) diet.

Proper education will be given about drug , method of taking medication and medication plan. Afterwards, a good rapport will be built up to take time to time follow up over telephone and visiting patient's place . Schedule appointment , hotline and follow up will be maintained properly. They will be requested to attend the Department of Physiology again on the 90th day, to have the assessment of all the above-mentioned study variables

Any patient, who failed to follow the study procedure exactly during study period, will be dropped and a new one will be included to fulfill the desired total sample number. That's why extended sample should be taken to fulfill the total sample number.

Collection of blood sample (Afroza 2015):

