The 6MWT will be performed at indoors, along a long, flat, straight, enclosed corridor with a hard surface that is seldom traveled. The walking course will be 30 meter in length which will be marked every 3 meter. The turnaround points will be marked with a cone. A starting line, which marked

the beginning and end of each 60 meter lap, will be marked on the floor using brightly colored tape.

The subject will be asked to walk at his own maximal pace along the corridor from the end, covering as much ground as he can, during the allotted time, without running. He will be also advised to take rest if he will be too exhausted to continue the test. Standard phrases at regular intervals (every 60 seconds) will be used, like: “you are doing well,” “keep up the good work”. At the same time he will be also informed about the past time and how much has left before the test was completed.

If any of the subjects developed chest pain, intolerable dyspnoea, leg cramps, staggering, diaphoresis or pale appearance the test will be immediately stopped and the subject will be dropped. Again, when any subject will complete the total study procedure (according to the exact study design), he will be congratulated for good effort.

STATISTICAL ANALYSIS:

The results will be expressed as mean with standard deviation (mean \pm SD).

The data will be statistically analyzed by a computer with SPSS (Version 16.0) using Chi-square test,(to know the qualitative difference between the observed and expected result).Spirometric variables, oxygenation variables, exercise tolerance variables and hematological variables will be found between two groups of patients. If the variables are normally distributed , statistical analysis will be done by parametric statistical test. But if it is not normally distributed then it will be transformed into natural logarithm and again into anti logarithm, to make it normally distributed, then parametric statistical test will be done. Independent sample ‘t’ test between two groups, paired Student’s ‘t’ test within two specific measurements of different durations of each group will be done.

In the interpretation of results, ≤ 0.05 level of probability (p) will be accepted as significant.

PUBLICATION POLICY

- ❖ Scientific article to be published in a scientific journal.
- ❖ Presentation in scientific seminar or conference orally or through poster presentation.
- ❖ Website dissemination through internet version of JBSP.

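### In the supplied text no primary outcome, deciding test or success rule is named, so 8 to 10 clinical outcomes, each tested between and within arms at p ≤ 0.05, can all be offered as support for vitamin D3

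*Combined protocol and SAP*

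**What the plan says.** The STATISTICAL ANALYSIS section states that "Spirometric variables, oxygenation variables, exercise tolerance variables and hematological variables will be found between two groups of patients". It specifies an independent-sample t test between groups and a paired t test "within two specific measurements of different durations of each group will be done". The only decision criterion is a ≤ "0.05 level of probability (p) will be accepted as significant". It does not say whether the between-group test uses day-90 values or changes.

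STUDY VARIABLES lists, without ranking:
- 5 spirometric indices (FVC, FEV1, FEV1/FVC, PEFR, FEF25-75)
- resting SpO2
- 6MWD and "Level of Dyspnea : Modified Borg Scale"
- 5 blood variables

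The alternative hypothesis is that vitamin D3 "administration improves lung function and exercise tolerance". Expected outcome likewise anticipates improvement in both together. The Rationale adds peripheral oxygen saturation as a third aim.

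The exercise measures differ from section to section:
- PROJECT SUMMARY: "exercise tolerance will be assessed by change in 6 Minute Walk Distance (6MWD) in 6 Minute Walk Test (6MWT". SpO2 and dyspnoea "will also be measured both before and after 6MWT to evaluate their change in both the groups".
- STUDY VARIABLES: 6MWD and dyspnoea.
- Specific Objectives: 6MWD is assigned to functional exercise capacity. SpO2 is measured with "level of dyspnea again after 6MWT, for the assessment of their exercise tolerance".

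The sample size of 46 (23 per arm) is given with no outcome, effect size or power, so a primary outcome cannot be inferred from it.

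**The concern.** With no ranking, deciding test or success rule, the result that supports vitamin D3 can be picked once the results are known. Three choices are open: which of 8 to 10 clinical outcomes, which test (between arms, or paired within the vitamin D3 arm), and how many positive results are needed. The listed 8 outcomes alone give 8 × 3 = 24 tests (one between groups, one paired in each arm).

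The paired test is a separate weakness. VITAMIN ADMINISTRATION and the text after STUDY VARIABLES have standard treatment prescribed to all patients. A change from day 0 to day 90 in the vitamin D3 arm therefore mixes any vitamin D3 effect with whatever both arms gain from treatment, repeat testing or time. Nothing in the plan prevents such a change from being reported as success.

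**Working it through.** **The plan's own figure.** The 46 cannot be reproduced, because no effect, SD or power is stated. For scale, at two-sided 0.05 and an assumed 80% power, 23 per arm detects (1.960 + 0.842) × √(2/23) = 0.83 SD by the normal formula, or 0.845 SD with the t distribution.

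**Count of clinical outcomes.** 5 + 1 + 2 = 8 from STUDY VARIABLES. Adding post-walk SpO2 and dyspnoea gives 10. Blood variables are left out.

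**Rule 1: any one significant between-group result counts, no true effect.** For k independent outcomes the risk is 1 − 0.95^k in either direction and 1 − 0.975^k for benefit.
- k = 8: 1 − 0.95^8 = 33.7%; benefit 1 − 0.975^8 = 18.3%
- k = 10: 1 − 0.95^10 = 40.1%; benefit 1 − 0.975^10 = 22.4%

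The documents give no correlations, so a common correlation ρ is assumed (normal simulation, 400,000 draws):

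| ρ | 8 outcomes (benefit) | 10 outcomes (benefit) |
|---|---|---|
| 0 | 34% (18%) | 40% (22%) |
| 0.5 | 25% (13%) | 29% (14%) |
| 0.7 | 19% (10%) | 21% (11%) |
| 0.9 | 12% (6%) | 13% (6%) |

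One named outcome would give 5% (2.5% for benefit).

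**Rule 2: at least one significant result in each of two domains** (5 spirometric, 2 exercise measures). With independence and no effect: (1 − 0.95^5) × (1 − 0.95^2) = 0.226 × 0.0975 = 2.2%. A true exercise effect of d SD shifts the exercise z statistics by d × √(23/2). The last row of the table has high correlation within a domain and none across.

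| Correlation within / across | No effect: either direction (benefit) | Exercise 0.5 SD, spirometry null: benefit | Exercise 0.845 SD, spirometry null: benefit |
|---|---|---|---|
| 0 / 0 | 2.2% (0.6%) | 7.5% | 11.5% |
| 0.5 / 0.5 | 4.4% (2.2%) | 8.7% | 9.0% |
| 0.7 / 0.7 | 5.4% (2.7%) | 7.4% | 7.4% |
| 0.9 / 0.9 | 5.8% (2.9%) | 5.1% | 5.1% |
| 0.9 / 0 | 0.7% (0.2%) | about 2% | 4.4% |

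With one named variable per domain and both required, the false claim needs the single null spirometric test to be significant for benefit, so it cannot exceed 2.5%. With no correlation across domains it is power × 2.5%: 0.38 × 2.5% = 1.0% at 0.5 SD and 0.80 × 2.5% = 2.0% at 0.845 SD. These are the like-for-like comparators for the last row.

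**Paired test in the vitamin D3 arm, no vitamin D3 effect.** If both arms improve by δ SD of change, the chance of significance for benefit comes from a noncentral t with 22 df and noncentrality δ√23. At assumed δ of 0.2, 0.3 and 0.4 it is 15%, 28% and 45% per outcome. These δ values are illustrative; the documents give none.

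**The case against.** The strongest defence is that the hypothesis supplies the rule: it joins the two domains with an and, Expected outcome does the same, and the any-one reading would let resting SpO2 alone confirm a hypothesis that does not mention oxygenation. This has force. A reader might infer from the omission that the trial carries a 34–40% false-positive rate. The documents do not support that: the figure needs both the any-one rule, which is the less natural reading, and independent outcomes, although FEV1/FVC is computed from two other listed variables.

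A reader might equally infer that the two-domain reading is always badly inflated, or that exercise tolerance has four measures. Neither is supported. With high correlation within domains and none across, the risk at a 0.5 SD exercise effect is about the 2.5% ceiling of the fixed rule. A count of four would need resting dyspnoea as an exercise measure, whereas Specific Objectives treats it as baseline breathlessness.

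What remains is that the hypothesis names no measure for either domain and does not say that both must be significant, and that the Rationale adds a third aim. The two-domain reading also leaves the paired test available as evidence.

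**Conclusion.** The concern holds as an omission with a conditional cost. How large the false-positive risk is depends on the rule the plan leaves open: 12–40% in either direction if any one outcome counts, and about 1–6% if one result per domain is needed and neither domain responds. If exercise improves and spirometry does not, it is about 2–12% for benefit at an assumed exercise effect of 0.5–0.845 SD, against at most 2.5% with named variables. All these ranges rest on assumed correlations and effects. The paired-test weakness needs no such assumption: the test has no control comparison.

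Two further inferences go beyond the evidence. One is that no primary outcome was ever set. Part of the document and several annexures were not available, including the one on the ClinicalTrials.gov application, so the finding covers the supplied text only. The other is that outcomes were chosen after the data were seen. The study period ends in February 2018 and the document is dated December 2018, which raises the question but does not settle it.

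**What to change.** 1. Name one outcome per domain. 6MWD is a natural choice for exercise, since PROJECT SUMMARY already uses it. FEV1 appears in the evidence cited in the Introduction and Rationale, but the plan ranks no spirometric index, so the choice is the sponsor's.
2. Compare each between arms at day 90 with adjustment for its baseline value, in place of the unadjusted t test.
3. State one success rule that requires the difference to favour vitamin D3. Either both outcomes reach two-sided p ≤ 0.05, or, if either alone may support a claim, use Holm (smaller p against 0.025, then the other against 0.05).
4. List all other clinical outcomes once as secondary, with estimates and 95% confidence intervals. Include SpO2, reconciled with the Rationale, and say whether post-walk SpO2 and dyspnoea are separate outcomes.
5. Make within-group paired tests descriptive.
6. If the data had been seen, label the hierarchy post hoc. That helps the reader but does not restore prespecification.

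No new data are needed, but this changes the test and costs power. Power with 23 per arm at assumed effects (correlation between the two outcomes 0–0.5; adjusted figures assume a baseline correlation of 0.5):

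| Rule | 0.5 SD unadjusted | 0.5 SD adjusted | 0.845 SD unadjusted | 0.845 SD adjusted |
|---|---|---|---|---|
| One outcome at 0.05 | 38% | 48% | 80% | 90% |
| Both at 0.05 | 14–22% | 23–31% | 64–69% | 81–83% |
| One outcome at Holm's 0.025 step | 28% | 37% | 71% | 83% |

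At 0.845 SD, baseline adjustment roughly recovers what requiring both outcomes costs. At 0.5 SD, power is low under every rule.

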FEV ₁ /FVC	(%)				
PEFR:	(L/S)				
FEF ₂₅₋₇₅	(L/S)				
MEF ₇₅	(L/S)				
MEF ₅₀	(L/S)				
MEF ₂₅	(L/S)				

(PV=Predicted Value, MV=Measured Value)

Variables	Before	After	Before	After
	(day 0)	(day 0)	(day 90)	(day 90)

Oxygen Saturation % (SpO₂)

Level of dyspnea (Borg Score)

Level of fatigue (Borg Score)

Total Distance (in meter) Walked In 6 Minute :

The Modified Borg Scale:

SCALE	SEVERITY
0	No Breathlessness At All
0.5	Very Very Slight (Just Noticeable)
1	Very Slight
2	Slight Breathlessness
3	Moderate
4	Somewhat severe
5	Severe Breathlessness
6	
7	Very Severe Breathlessness
8	
9	Very Very Severe (Almost Maximum)
10	Maximum

Hematological variables:

Serum 25(OH)D ng/ml

Serum PTH pg/ml

Serum Ca²⁺ mg/dl

Serum IU/L

Alkaline
phosphat
ase

Serum IU/L

SGPT

Serum mg/dl

Creatini
ne

Fasting mg/dl

blood
glucose

Serum %

HbA1c

Serum (mg/dl)

Choleste
rol

Serum (mg/dl)

TG

Serum (mg/dl)

HDL

Serum (mg/dl)

LDL

Serum (mg/dl)

PO₄³⁻
